We aim to characterize the safety and efficacy of a topical preparation of *Lactobacillus sp.*, honey, and turmeric in an emollient base in restoring the scalps of those with dry scalp to more closely resemble the healthy scalps.

2. STUDY DESIGN AND SYNOPSIS:

This pilot study consists of participants diagnosed with dry scalp. Participants will receive the required topical vehicle with the treatment condition (containing dead bacteria) on their scalp. This study will consist of 15-40 participants' ages 1 years old to 17 years old and 20-40 participants 18 and older with a clinical diagnosis of dry scalp. Participants will be recruited either while visiting a dermatologist for a standard office visit, while visiting a pediatrician for a standard office visit, or by coming into Children's Healthcare Associates, Medical Dermatology, or our Northwestern research office to be assessed by a physician. Each study visit will take approximately 15-20 minutes.

No randomization will occur, as all participants will receive the active treatment. Each adult participant will apply the active treatment once daily for a study period of 14 days and discontinue using all other scalp management therapies. Each child participant (with the help of a caregiver, if needed) will apply the active treatment once every 2 to 3 days for a study period of 14 days and discontinue using all other scalp management therapies.

The primary goal of this study is to determine the safety and effectiveness of *Lactobacillus sp.*, honey, and turmeric in reducing dry scalp symptomology.

There are three goals in the comparison of these conditions:

- The first is to find the effectiveness of the active treatment in improving clinical disease severity. To accomplish this, an investigator will assess the severity of dry scalp before and after the treatment period using the 11-point flaking scale (Neumann 1996), respectively.
- The second goal is to determine whether the active treatment is safe. This will be accomplished by contacting the patient via over the phone and through daily emails designed to document adverse events and Overall Safety Score. The Overall Safety Score is a 4-point assessment ranging from "no signs of irritation" (0) to "patient discontinued due to irritation" (3). Participants will be asked about the Overall Safety score at the halfway point and the end point of the study.
- The third exploratory goal is to determine whether the microbiome can be changed. This will be

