Participants will be supplied with the scalp treatment and relevant instructions. Participants will be instructed to apply the preparation to their scalp. Adults will apply the scalp treatment on the site of active dry scalp once per day at home at a consistent time, every day for 14 days. Children will apply the hair care regimen at home at a consistent time two to three times a week over a 14-day period. -. Participants will be instructed to discontinue their regular scalp-care therapies. Adult participants will be contacted daily via email or telephone regarding scalp care regimen, usage of treatment, and any adverse events. Child participants will be contacted weekly via email or text regarding scalp care regimen, usage of treatment, and any adverse events. One week from the baseline visit (7 days), the participant will be contacted via phone, text or email to complete surveys regarding treatment experience and to confirm correct usage of treatment. Fourteen days following the baseline visit, adult participants will be seen, where repeat scalp cultures will be obtained via the swab and RODAC methods, and a repeat scalp flaking survey (IGA) (with photographs) will be assessed by a physician. Final experience surveys will be administered via REDCap. Fourteen days following the baseline visit, child participants will attend a secondary visit, where a physician will assess the participants' scalp and re-evaluate the IGA placement.

Study Schema

VISIT 1: (baseline)

- Recruitment and electronic informed consent of participants via REDCap.
- Obtain baseline scalp culture skin swabs from participant for microbiome diversity analysis.
- Obtain baseline scalp cultures from participant via RODAC method to obtain initial bacterial burden level. The RODAC (Replicate Organism Detection and Counting) method is used to measure the number of colony forming units (CFU) per skin surface area. The primary purpose of the RODAC method is to monitor presence and number of microorganisms as determined by the appearance of colonies on the surface of an agar medium.
- Local scalp flaking survey performed to the participant by investigator. Photographs will be taken.
- Administer baseline demographics survey via REDCap.
- Demonstrate/teach patients the treatment regimen. The treatment for adults will be applied daily for 14 days for 5 minutes. The treatment for children will be applied 2 to 3 times a week over the course of 14 days for 5 minutes.

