- Instruct adult participants to respond to the daily scalp care emails or phone calls. Instruct child participants to weekly scalp care emails, text messages, or phone calls.- Provide participants with all study materials, including instruction handout.
- Instructions for adults will be given stating: Wash your hands and make sure scalp/hair is dry, and then apply the treatment to your entire scalp. Massage the treatment in, wait around seven minutes, and then rinse it from your scalp. Please be sure to apply the treatment daily. Instructions for children will be given stating: Wash your hands and make sure scalp/hair is dry, and then apply the treatment to your entire scalp. Massage the treatment in, wait approximately five minutes, and then rinse it from your scalp. Please be sure to apply the treatment 2 to 3 times a week.

FOLLOW-UP:

- Study coordinator will contact participant or caregiver via phone or email daily to ensure safety of treatment regimen. [name] will follow-up with patients if adverse events are reported.
- Quality of life and overall safety score surveys will be sent to participants at the 7 day mark.

VISIT 2 at Lurie Children's, Northwestern University, or Medical Dermatology Associates of Chicago: (14 days after baseline)

- Obtain scalp culture skin swabs from patient for microbiome diversity analysis.
- Obtain scalp cultures from patient via RODAC method to obtain final bacterial burden level.

- Local scalp flaking survey performed to patient by investigator. Additional photographs will be taken.
- Ask participants to fill out the follow-up questionnaire via REDCap during the visit on a study iPad.

Events performed outside of patient visits:

-Skin swabs and RODAC plates will be transported from the collection site to the laboratory of [name] or to [name] lab at Rush University. The team will use an insulated carrier to transport the samples directly following each visit.

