6.1. Primary Outcome Measures

The primary objective is to determine the safety and efficacy of YoBee in improving dry scalp conditions. Efficacy will be determined using the Investigator's Global Assessment (IGA) scale (Table 1), a 5-point assessment ranging from clear (0) to severe disease (4) and the Total Severity Scale (TSS) (Table 2), an assessment that averages erythema, scaling, and pruritus severity scores of scalp lesions. The TSS uses a 4-point scale ranging from none (0) to severe (3). Lastly, photographs of the scalp will be collected before and after treatment. Safety will be determined by contacting the patient via over the phone or through email to document adverse events and Overall Safety Score. The Overall Safety Score (Table 4) and the reporting of adverse events throughout the study will measure the safety of YoBee. The Overall Safety Score is a 4-point assessment ranging from “no signs of irritation” (0) to “patient discontinued due to irritation” (3). Participants will include the Overall Safety Score assessment in their daily journal.

An exploratory aim of this study is to find whether YoBee changes the microbiome after use for a dry scalp condition to more closely resemble healthy scalps. This will be accomplished by obtaining swab samples from the participants' scalps, before and after the treatment period. The samples will be analyzed using 16s RNA sequencing and internal transcribed spacer (ITS) sequencing. Additionally, the change in colony count of bacterial and fungal colonies on the scalp before and after the treatment will be assessed using the Replicate Organism Detection and Counting (RODAC) method. Finally, ScalpDex, a validated instrument, will assess the change in quality of life of participants. ScalpDex is a 23 question survey that will be administered electronically via RedCap to participants.

7. DATA DISCLOSURE AND SUBJECT CONFIDENTIALITY:

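### The protocol conflicts on whether adverse events in children are solicited weekly or daily; the weekly version risks under-recording mild irritation in children

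*Combined protocol and SAP*

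**What the plan says.** Section 5 (Study Procedures) sets the contact rule by age in adjacent sentences. For adults: "Adult participants will be contacted daily via email or telephone regarding scalp care regimen, usage of treatment, and any adverse events". For children: "Child participants will be contacted weekly via email or text regarding scalp care regimen, usage of treatment, and any adverse events". The Visit 1 list in the same section repeats the split: "Instruct child participants to weekly scalp care emails, text messages, or phone calls". The paragraph on staff roles at the end of section 5 describes daily calls or emails about adverse effects for adults only.

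Other places read differently. The Follow-up list in section 5 says "Study coordinator will contact participant or caregiver via phone or email daily to ensure safety of treatment regimen"; naming the caregiver brings in the children. Section 2 describes "daily emails designed to document adverse events and Overall Safety Score", and section 6.1 says "Participants will include the Overall Safety Score assessment in their daily journal". Neither is limited to adults.

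The Overall Safety Score has its own timing statement in section 2: "Participants will be asked about the Overall Safety score at the halfway point and the end point of the study". That has no age split, and the Follow-up list sends the score to participants at day 7. Section 6.1 makes safety part of the primary objective, measured by this score and by adverse events reported during the study.

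**The concern.** Adverse-event reporting is part of the primary safety outcome, and the plan does not settle how it is collected in children. Staff could follow either version. If they follow the age-specific sentences, the same outcome is collected with a recall window of about a day in adults and up to a week in children. Section 9 names mild irritation as the possible risk, and mild complaints are plausibly among those more easily lost when someone is asked to look back over a week. Parents answer the surveys for all children, although those aged 12 to 17 apply the product themselves, so a parent may not have seen a teenager's reaction.

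At stake is how a low or zero count in children would be read. If solicitation was sparse, the count is less reassuring than it looks. Section 10 contains no safety analysis, so nothing rules out pooling or comparing event rates that were gathered in different ways.

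**Working it through.** The plan states no adverse-event rate, no sample-size basis for safety and no planned comparison of children with adults, so there is no figure of its own to reproduce. The only power statement (section 10.1) concerns the severity score.

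**1. The statements side by side**

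| Place | Adults | Children |
|---|---|---|
| Section 5, main text | daily | weekly |
| Section 5, Visit 1 instructions | daily | weekly |
| Section 5, staff roles | daily | not mentioned |
| Section 5, Follow-up list | daily | daily (caregiver named) |
| Section 2, adverse-event emails | daily, no age split | daily, no age split |
| Section 6.1, journal | daily, no age split | daily, no age split |

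The age-specific sentences on contact agree with each other. The Follow-up list contradicts them directly; sections 2 and 6.1 contradict them by not limiting daily collection to adults.

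**2. Prompts over the 14-day period**

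- Weekly version: adults 14/1 = 14, children 14/7 = 2, a ratio of 7 to 1. The longest recall is about 1 day against 7 days.
- Daily version: 14 against 14, with no difference.

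**3. Exposure.** Adults apply the product 14 times. Children apply it 2 × 2 = 4 to 2 × 3 = 6 times under section 5 (two to three times a week), or 5 to 7 times under section 2 (once every 2 to 3 days). These two descriptions also need reconciling. Under the weekly version, children would have one prompt per 4/2 = 2 to 7/2 = 3.5 applications, against one per application in adults.

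**4. Possible size, on assumed inputs.** Let p be the true 14-day risk in children and c the share of affected children whose event is recorded under weekly contact, relative to daily. Neither is in the documents. I assume p = 20% and c = 0.5 to 0.8.

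- Recorded rate = p × c: 0.20 × 0.5 = 10% to 0.20 × 0.8 = 16%. With p = 10% the range is 5-8%; with p = 30% it is 15-24%.
- Affected children missed = n × p × (1 − c): 0.6 to 1.5 at n = 15, and 1.6 to 4.0 at n = 40.
- Chance that 15 children yield no recorded event: 0.80^15 = 3.5% with full capture, 0.84^15 = 7.3% with c = 0.8, and 0.90^15 = 20.6% with c = 0.5.
- One-sided 95% upper bound on risk after zero recorded events, (1 − 0.05^(1/n))/c: at n = 15, 18.1% with full capture, 22.6% with c = 0.8 and 36.2% with c = 0.5. At n = 40 the figures are 7.2%, 9.0% and 14.4%.

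**5. Could a lower child rate be attributed to recall?** Assume equal, independent risk per application and an adult 14-day risk of 20%. The child risk from exposure alone is 1 − 0.80^(k/14): 6.2% at k = 4, 7.7% at k = 5, 9.1% at k = 6 and 10.6% at k = 7. Exposure alone could therefore produce a gap as large as the one that halved capture would give (20% against 10%). Nor could the study detect that gap reliably: at 40 per group, power to distinguish 20% from 10% is about 24% (two-sided 5%).

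**The case against.** The strongest reply is that the plan may already provide daily collection in children. The Follow-up list says so, and section 6.1 gives the journal to participants without an age limit. This stands. A reader who sees only the age-specific sentences might infer a settled weekly rule, and the documents do not support that. Nor would unequal solicitation survive every correction of the wording: if the text is reconciled to daily contact for all, the difference disappears.

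Several safeguards also count. The Overall Safety Score, which grades irritation, is asked at the halfway and end points without an age split. Children are seen by a physician at day 14. The principal investigator is named as the contact for adverse events, so a caregiver need not wait to be asked. Parents apply the product to those aged 1 to 11. Between 5 and 10 adults complete the study before any child enrols. These limit the consequences, but they do not settle how often adverse events are solicited between assessments.

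A reader might also infer that the plan expects irritation that settles within a day or two. Section 9 says only that mild irritation is possible and should be minimal; it gives no duration. The recall argument is therefore plausible, but the text does not establish it.

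**Conclusion.** The supportable finding is a conflict over how often adverse events are solicited in children, on an outcome that belongs to the primary objective. If the weekly version is followed, children have about 2 prompts against 14, with recall of up to 7 days against about 1, and under-recording of mild irritation in children is a likely risk of unknown size. The 10-16% recorded from a true 20%, and the upper bound rising from 18.1% to as much as 36.2% after no events in 15 children, illustrate assumed capture of 50-80%; they are not estimates for this trial.

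A reader might go further and conclude that the child rate is in fact under-counted relative to adults. The documents do not support that: they give neither an event rate nor a capture rate, they plan no such comparison, and any comparison would be confounded by exposure, age and parent reporting.

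**What to change.** - Reconcile section 2, section 5 (main text, Visit 1, Follow-up and staff roles) and section 6.1 to one adverse-event collection schedule, with the same question and the same recall window in both cohorts. The daily journal already named in 6.1, or an automated daily REDCap item completed by the child or caregiver, would serve. State the timing of the Overall Safety Score once.
- Report adverse events separately for children and adults, with the number of contacts made and answered, the recall window, and rates per participant and per application.
- If the schedules stay unequal, base any pooled or compared safety result only on the 7-day and 14-day assessments common to both groups.
- Reconcile the two descriptions of how often children apply the product, since the per-application rate depends on them. Which applies is for the sponsor to state.

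The cost is a wording amendment and, relative to the weekly version, about 14 − 2 = 12 more short entries per child. The downside is a small extra burden on caregivers and possibly more minor events reported.

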9. SAFETY ASSESSMENT

All of the ingredients contained in our topical formulation are either foods or commonly used in cosmetics and skin care products. As such, we have minimal reason to believe that participants will experience major adverse events from treatment. There may be a risk of mild irritation, given the nature of already inflamed skin, but this should be minimal as compared to current accepted topical treatments for dry scalp. This study utilizes dead *Lactobacillus* species to eliminate the risk of growth and thus, the risk of new disease or symptomatology. Furthermore, dead bacteria are easier to store and offer a longer shelf life, eliminating the risk of application of an unknown size or species of bacteria.

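### No adverse-event contact is scheduled after the day-14 visit, so reactions that begin after the last applications may go unrecorded

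*Combined protocol and SAP*

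**What the plan says.** Safety is part of the primary goal (Section 2) and of the primary objective (Section 6.1). It is measured by adverse events and the Overall Safety Score. Section 9 names the expected problem: "There may be a risk of mild irritation, given the nature of already inflamed skin".

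**Treatment and visit.** Section 5 has adults apply the product "once per day at home at a consistent time, every day for 14 days". For children it says: "Children will apply the hair care regimen at home at a consistent time two to three times a week over a 14-day period". Section 2 describes the child schedule differently, as one application every 2 to 3 days. The schema in Section 5 heads the final visit "VISIT 2 at Lurie Children's, Northwestern University, or Medical Dermatology Associates of Chicago: (14 days after baseline").

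**Safety contacts up to day 14.** The narrative of Section 5 says "Adult participants will be contacted daily via email or telephone regarding scalp care regimen, usage of treatment, and any adverse events", and for children "Child participants will be contacted weekly via email or text regarding scalp care regimen, usage of treatment, and any adverse events". The follow-up part of the schema says instead: "Study coordinator will contact participant or caregiver via phone or email daily to ensure safety of treatment regimen". Section 2 asks for the Overall Safety Score at the midpoint and at the end. The schema sends the score survey at day 7 only. Section 6.1 puts the score in a daily journal.

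**Day 14.** A physician assesses the scalp of adults and children. The Visit 2 list ends with "Ask participants to fill out the follow-up questionnaire via REDCap during the visit on a study iPad". The content of that questionnaire is not described, and the list names neither the Overall Safety Score nor an adverse-event question.

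**After day 14.** The schema's list of events outside visits covers only sample transport. No further participant contact appears. Section 5 does provide for follow-up of events once reported, and makes the principal investigator the primary contact for adverse events.

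**The concern.** Observation stops at about the time treatment stops. The most recent applications, which come when cumulative exposure is greatest, have the least time in which a reaction can show itself and be recorded. A participant whose skin reacts a day or two after Visit 2 has no planned occasion to say so.

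Any loss of this kind runs one way, because unrecorded events can only lower the count. The study has a single arm, so no control group would show the same loss. The groups are also small: one unrecorded participant with an event would shift the observed rate by 1/40 = 2.5 to 1/20 = 5 percentage points in 20 to 40 adults, and by 1/40 = 2.5 to 1/15 = 6.7 points in 15 to 40 children. These figures show what one event is worth. They do not estimate how many are missed.

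**Working it through.** The documents give no adverse-event rate, no time to onset and no safety follow-up period, so there is no figure of the plan's own to reproduce. The check is calendar arithmetic.

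**Inputs**
- Adults: 14 applications, one per day (Section 5).
- Children: 2 to 3 a week for 2 weeks gives 2 × 2 = 4 to 3 × 2 = 6 applications (Section 5). Every 2 or 3 days gives 7 or 5 in the patterns below (Section 2).
- Last scheduled contact: day 14 (Section 5).
- First application: not stated, so day 0 and day 1 are both tried (assumption).
- Onset window w: 24, 48 or 72 hours (assumption; the documents give none).

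**Formula.** For an application on day d, the observation time is g = 14 − d days. The application is incompletely observed if 24 × g < w.

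**Adults**

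| First application | Last application | Gap to visit | Under 24 h | Under 48 h | Under 72 h |
|---|---|---|---|---|---|
| Day 0 | Day 13 | 1 day | 0 of 14 (0%) | 1 of 14 (7%) | 2 of 14 (14%) |
| Day 1 | Day 14 | 0 days | 1 of 14 (7%) | 2 of 14 (14%) | 3 of 14 (21%) |

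**Children**

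| Pattern | Applications | Gap to visit | Under 24 h | Under 48 h | Under 72 h |
|---|---|---|---|---|---|
| Every 2 days from day 0 | 7 | 2 days | 0 | 0 | 1 |
| Every 2 days from day 1 | 7 | 1 day | 0 | 1 | 1 |
| Every 3 days from day 0 | 5 | 2 days | 0 | 0 | 1 |
| Every 3 days from day 1 | 5 | 1 day | 0 | 1 | 1 |
| Days 0, 3, 7, 10 (illustration of twice weekly) | 4 | 4 days | 0 | 0 | 0 |

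The ranges are therefore 0 to 3 of 14 adult applications and, in these patterns, 0 to 1 of a child's.

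Gaps are counted in whole days. The documents give no clock times, and a visit earlier in the day than the usual application would shorten each gap by some hours. That can tip an application lying exactly on the boundary into the incomplete group.

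**Effect of one later contact.** With the same 72-hour window, the number of adult applications still incompletely observed (day-0 start, day-1 start) is 2 and 3 if collection ends on day 14, 0 and 1 with a contact on day 16, and 0 and 0 with a contact on day 17.

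**The case against.** A reader might infer that reactions to the last applications are never asked about. The documents do not support that. Adults are contacted daily about adverse events, Section 2 plans the Overall Safety Score at the end point, and a physician examines the scalp on day 14. A reaction to a day-12 or day-13 application that is evident by the visit falls within planned collection. The gap is confined to onset after the visit.

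A reader might also infer that safety is undercounted as a matter of fact. That is not shown. The percentages above count applications, not events. An adult has had 11 or more earlier applications of the same rinse-off product, with daily questioning, and is missed only if the first reaction begins after day 14. With a day-0 start and 1-day onset, no adult application is incompletely observed. The same holds for a child whose last application is 3 or more days before the visit. So it cannot be said that every participant is affected.

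Nor does the questionnaire sentence say that adverse-event collection ends at Visit 2. Section 6.1 speaks of reporting over the whole study, and Section 13.1 on prompt submission to the IRB sets no cut-off. The principal investigator's role as adverse-event contact may give participants a way to report unprompted. Finally, the visible text passes from Section 11 to Section 13, so a reporting rule in Section 12 can be neither assumed nor excluded.

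All of this stands, and it limits the point to what is scheduled. It does not supply a planned contact after the visit. An unprompted route is weaker than a question asked of everyone. The day-14 check is itself loosely specified, since the Visit 2 list names neither the score nor an adverse-event question.

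**Conclusion.** The point holds in a limited form. In the visible plan, the last scheduled safety contact falls about 0 to 1 day after the last adult application, and reactions that begin later have no scheduled collection. Under an assumed onset window of 1 to 3 days, 0% to 21% of adult applications and about 0 to 1 of a child's roughly 4 to 7 are incompletely observed. The result rests on that window, on a first application on day 0 or day 1, on whole-day counting, and on Section 12 containing no later contact.

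The direction of any error is clear: toward a finding of safety. Its size cannot be computed, so the supportable wording is that events may be undercounted. It is worth acting on because safety is a primary outcome and the remedy is cheap.

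Two contradictions can be shown from the text alone and bear on safety capture during treatment as well. The Overall Safety Score is timed in three ways (Section 2, the Section 5 schema, Section 6.1). Contact with children is weekly in the Section 5 narrative, but the schema has the participant or caregiver contacted daily.

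**What to change.** 1. Check whether Section 12 already provides a safety contact after treatment. If it does, cross-refer to it from the schema in Section 5.
2. If it does not, add one email, text or phone contact a few days after the last application. On the whole-day count above, day 17 or later gives every scheduled adult application at least 72 hours. Ask about adverse events and the Overall Safety Score since Visit 2.
3. Send the same contact to participants who stop early, covering the time since they stopped.
4. State the adverse-event collection window and the day of the first application, and say that events reported at the added contact count in the safety result.
5. Name the Overall Safety Score and an adverse-event question in the Visit 2 list.
6. Reconcile the timing of the score (Sections 2, 5 and 6.1), the frequency of contact with children (within Section 5) and the two descriptions of the child application schedule (Sections 2 and 5). This point takes no view on which schedule is right.

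The cost is a short amendment, one more automated message per participant through channels already in use, and close-out a few days later. No visit is added.
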